## 1.0 PROTOCOL SUMMARY AND/OR SCHEMA

This is a single-center, single-arm phase II study to evaluate the efficacy and safety of the anti-IL-5R $\alpha$  chimeric monoclonal antibody benralizumab for the treatment of eosinophil-related cutaneous adverse events (ercAEs) resulting from immunotherapies or targeted therapies. Forty eight (48) patients will be enrolled and the estimated time to completion is 2 years. The primary endpoint for the study is the percent reduction in CTCAE grade 2/3 eosinophil-related cutaneous adverse events to grade  $\leq 1$ . Eosinophil-related cutaneous adverse events are defined as maculopapular rash, pruritus/urticaria, bullous pemphigoid, or DRESS syndrome that are associated with blood eosinophil counts of at least .3 K/mcl. Secondary endpoints are safety and tolerability of benralizumab, calculated rash body surface area (BSA), relative dose intensity (RDI) of anticancer therapy, measurement of patient-reported quality of life, the ability to continue anticancer agents, effects on corticosteroid naïve and dependent/refractory ercAEs, the need for additional supportive care interventions (i.e. corticosteroids, antihistamines), and reduction in blood and skin eosinophils. An exploratory endpoint is analyzing eosinophils and Th2 immune pathway blood biomarkers ( IFN- $\gamma$ , IL-1 $\beta$ , IL-2, IL-4, IL-5, IL-6, IL-8, IL-10, IL-12p70, IL-13, TNF- $\alpha$ , tryptase) that correlate with benralizumab efficacy. Patients with a diagnosis of solid or hematologic cancers undergoing treatment with checkpoint inhibitors (CPIs) or targeted therapies with a grade 2/3 cutaneous adverse associated with blood eosinophil counts of at least .3 K/mcl will be treated with benralizumab 30mg once every 4 weeks for the first 3 doses (Week 0/Day 1, Week 4/Day 28, and Week 8/Day 56), followed by once every 8 weeks for 3 additional doses (Week 16/Day 112, Week 24/Day 168, and Week 32/Day 224). CTCAE v5.0 ercAE assessments will be done at baseline and then at Week 2/Day14, Week 4/Day 28, and Week 8/Day 56, Week 16/Day 112, Week 24/Day 168, Week 32/Day 224 and 4 weeks post-last dose. Patients may remain on study until ercAE progression or unacceptable toxicity from benralizumab for up to 32 weeks.

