### Secondary objectives

- To investigate changes in adverse event-related quality of life using patient-reported questionnaires (PRO-CTCAE, Skindex 16).
- To investigate the safety/tolerability of benralizumab in patients with eosinophil-related cutaneous adverse events.
- To investigate the need for supportive medications (corticosteroids, antihistamines, immunosuppressants) in patients treated with benralizumab.
- To investigate the effect of benralizumab on subsequent planned cycles of checkpoint inhibitors (CPIs), or targeted therapies.
- To compare the effect of benralizumab on corticosteroid naïve and corticosteroid dependent/refractory ercAEs.

- To correlate the percent reduction in blood absolute eosinophil numbers and skin histology with clinical response to benralizumab.
- To investigate change in body surface area (BSA) of ercAE to quantify change in affected area in response to benralizumab over time.
- To investigate relative dose intensity (RDI) and compliance of patients' culprit anticancer therapy for the duration of the trial.

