## 3.0 BACKGROUND AND RATIONALE

### Background on eosinophil related cutaneous adverse events

In areas where helminth exposure is uncommon, medication-related drug reactions are a common cause of peripheral and blood eosinophilia (Ramirez and Frias, British Pharmacol Soc 2017). In the absence of systemic involvement, this condition generally constitutes a drug effect that can be caused by a myriad of medication classes, such as penicillin and sulphonamide drugs, and resolves upon drug discontinuation (Khoury and Bochner, JACIP 2018). In the oncology setting, eosinophil-related cutaneous adverse events (ercAEs) are also frequent (10-20%) (Fischer et al, Am J Dermatopathol 2015; Lucas-Truyols et al, Acta Dermosilicof 2017; Fujisawa et al, J Dermatol Sci 2017), but their impact is greater: they result in interruption or discontinuation of life-prolonging antineoplastic agents, negatively affect a patient's quality of life, may affect other organs (i.e. liver and kidneys as part of the Drug Rash with Eosinophilia and Systemic Symptoms (Cho et al, Int J Mol Sci 2017)), and usually require treatment with corticosteroids which carry their own set of toxicities in an already vulnerable patient population. Indeed, in oncology drug development trials, dermatologic toxicities are a dose-limiting toxicity in 2.4% of cases (Drilon et al, Cancer 2016). There are no FDA approved therapies for ercAEs, and whereas off-label use of corticosteroids and interruption of the offending agent may be effective in most patients, there are no additional therapeutic options for patients with corticosteroid dependent/refractory ercAEs.

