It can thus be argued that benralizumab is capable of killing eosinophils via a dual mechanism: the blockade of IL-5-mediated survival of these cells and the enhancement of eosinophil apoptosis induced by activation of the FcYRIIIa receptor of NK cells. By acting via such very powerful modalities, benralizumab rapidly and effectively depletes eosinophils in patients with asthma, thereby drastically reducing cell counts in both airways and peripheral blood. Benralizumab was recently approved by US FDA for the add-on biological therapy of severe eosinophilic asthma. A meta-analysis referring to 1951 subjects with eosinophilic asthma, enrolled in several different phase 1, 2, and 3 randomized controlled trials, demonstrated that, when compared to placebo, benralizumab induced significant score improvements of asthma control questionnaire-6 (ACQ-6) and asthma quality of life questionnaire (AQLQ) and enhanced Forced expiratory volume (FEV1) and also decreased the annual rate of disease exacerbations.

In the 52-week Phase 2 dose-ranging trial, asthma patients received 1 of 3 doses of benralizumab [2 mg (n=81), 20 mg (n=81), or 100 mg (n=222)] or placebo (n=222). All doses were administered every 4 weeks for the first 3 doses, followed by every 8 weeks thereafter. Median blood eosinophil levels at baseline were 310, 280, 190 cells/µL in the 2, 20, and 100 mg benralizumab and placebo groups, respectively. Dose-dependent reductions in blood eosinophils were observed. At the time of the last dose (Week 40), median blood eosinophil counts were 100, 50, 40, 170 cells/µL in the 2, 20, and 100 mg benralizumab and placebo groups, respectively.

A reduction in blood eosinophil counts was observed 24 hours post dosing in a Phase 2 trial. In Trials 1 and 2, following subcutaneous (SC) administration of benralizumab at the recommended dose blood eosinophils were reduced to a median absolute blood eosinophil count of 0 cells/µL. This magnitude of reduction was seen at the first observed time point, 4 weeks of treatment, and was maintained throughout the treatment period.

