## 6.0 CRITERIA FOR PARTICIPANT ELIGIBILITY

### 6.1 Participant Inclusion Criteria

- Patients must have pathologically or cytologically confirmed solid or hematologic cancers.  
OR
- Patient is receiving alpelisib for PIK3CA-Related Overgrowth Spectrum disorder.
- Female and male aged 18 to 85 years, inclusively, at the time of Week 0/Day 1 of treatment.
- Patients must have a therapy-related CTCAE grade 2/3 (See Appendix A) cutaneous adverse event defined as any cutaneous reaction listed below and blood eosinophil counts of at least .3 K/mcl.
  - Rash maculo-papular
  - Bullous dermatitis
  - Pruritus
  - Urticaria
  - Eczema
- Patients must plan to continue on culprit drugs (cancer patients).
- Patients planning to receive alpelisib indicated for PIK3CA-Related Overgrowth Spectrum disorder OR patients receiving immunotherapy and/or targeted therapy, including but not limited to the following agents, will be eligible for inclusion:
  - Immunotherapies: ipilimumab, nivolumab, pembrolizumab, avelumab, durvalumab, atezolizumab, tremelimumab.
  - Targeted therapies: trastuzumab, pertuzumab, alpelisib, osimertinib, everolimus, temsirolimus, sorafenib, regorafenib.
- Patients using topicals/orals for indication of skin rash/pruritus for at least 7 days should continue using these drugs for the study duration.
- Adequate bone marrow, liver and renal function:
  - Total bilirubin  $\leq$  1.5 x the upper limit of normal (ULN)
  - Alanine aminotransferase (ALT) and aspartate amino-transferase (AST)  $\leq$  2.5 x ULN ( $\leq$  5 x ULN for subjects with liver involvement of their cancer)
  - Alkaline phosphatase  $\leq$  2.5 x ULN ( $\leq$  5 x ULN for subjects with liver involvement of their cancer)
  - Serum creatinine  $\leq$  1.8 xULN or calculated creatinine clearance  $>45$  ml/min

- Platelet count > 50 K/mcL, hemoglobin (Hb) > 8 g/dL, absolute neutrophil count (ANC) > 1.0 K/mcL. Blood transfusion to meet the inclusion criteria will not be allowed.
- ECOG performance status 0-1 (see Appendix C).
- Subjects must be able to understand and be willing to sign the written informed consent form. A signed informed consent form must be appropriately obtained prior to the conduct of any trial-specific procedure.
- Female patients are authorized to participate if they meet the following criteria:
  - Women of child bearing potential must meet both of the following conditions:

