## 10.0 TREATMENT/INTERVENTION PLAN

- Benralizumab 30mg as a subcutaneous injection will be administered by a healthcare professional at once every 4 weeks for the first 3 doses (Week 0/Day 1, Week 4/Day 28, and Week 8/Day 56), followed by once every 8 weeks for 3 additional doses (Week 16/Day 112, Week 24/Day 168, and Week 32/Day 224), per the labeling instructions.

- Patients will also have a comprehensive physical examination at Week 0/Day 1
- Skin examination prior to benralizumab administration will be completed at Week 0/Day 1, Week 4/Day 28, Week 8/Day 56).

- Phlebotomy for CBC w differential at every visit (Screening, Week 0/Day 1, Week 2/Day 14, Week 4/Day 28, Week 8/Day 56, Week 16/Day 112, Week 24/Day 168, Week 32/Day 224, and 4 Weeks post-last dose).
- Total body photography at Screening, Week 0/Day 1, Week 4/Day 28, Week 8/Day 56,.
- Research blood collection for biomarker analysis (MSD Panel and IL-5) on Week 0/Day 1, Week 4/Day 28 and Week 8/Day 56:
  - Approximately 10 mL of blood will be collected in a green top sodium heparin Vacutainer tube. This sample will be sent to the Immune Monitoring Facility (IMF).
  - Approximately 4 mL of blood will be collected in a lavender top tube (with EDTA). This sample will be sent to Mayo Clinic.

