**Safety and tolerability of benralizumab:** This endpoint will be measured in terms of CTCAE v5.0 ercAE. The proportion of patients with different grade categories (0, 1, 2 etc) will be assessed at each study time point along with exact binomial confidence intervals. Patients progressing to grade 4 ercAE will be removed from the study (Section 12.0). The proportion of such patients at each time point will be reported. The proportion of patients having a reduction and the proportion having an increase in ercAE grade category will be reported.

**Need for supportive medication:** The proportion of patients requiring supportive medications such as corticosteroids, antihistamines and immunosuppressants will be reported at each time point along with exact binomial confidence intervals.

**Effect of benralizumab on subsequent planned cycles of checkpoint inhibitors (CPIs) or targeted therapies:** We will measure changes in blood eosinophil levels between baseline and cycles of various planned treatments for these patients, and report the mean, standard deviation, range and number of patients scheduled to receive different therapies.

**Effect of benralizumab on corticosteroid naïve and corticosteroid dependent/refractory ercAEs:** Corticosteroid naïve patients are those not receiving corticosteroids for 14 days since Week 0/Day 1 of benralizumab treatment. Corticosteroid dependent/refractory ercAEs are patients that are on prednisone 10mg a day or greater at the initiation of study. We will report the number of corticosteroid naïve and dependent/refractory ercAE patients, measure change in blood eosinophil levels between Week 0/Day 1 and Week 8/Day 56, report descriptive statistics such as mean, standard deviation and range in these groups of patients.

**Effect on eosinophil counts:** Changes in eosinophil counts will be calculated and reported as percent reduction +/- standard deviation. In addition to comparing baseline and end-of-study percent change in eosinophils, we will also compare percent changes across baseline ercAE categories and end-of-study ercAE categories. We will use regression models to examine the association between longitudinal measurements of percent change in eosinophils at Week 0/Day 1, Week 2/Day 14, Week 4/Day 28, and Week 8/Day 56, Week 16/Day 112, Week 24/Day 168, Week 32/Day 224 and 4 weeks post-last dose and longitudinal measurements of ercAE categories.

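### The secondary analysis of subsequent planned cycles measures blood eosinophils and patients scheduled, so it cannot show whether culprit-drug cycles were given, delayed, reduced or stopped

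*Combined protocol and SAP*

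**What the plan says.** Section 2.0 lists as a secondary objective: "To investigate the effect of benralizumab on subsequent planned cycles of checkpoint inhibitors (CPIs), or targeted therapies". The protocol summary (Section 1.0) lists a related secondary endpoint, "the ability to continue anticancer agents", and Section 4.1 repeats it in similar words.

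In Section 14.1, under Secondary endpoints, the paragraph headed with the effect on subsequent planned cycles states the whole analysis in one sentence. It begins "We will measure changes in blood eosinophil levels between baseline and cycles of various planned treatments for these patients" and ends by saying that the team will "report the mean, standard deviation, range and number of patients scheduled to receive different therapies". Section 14 gives no analysis under the name of ability to continue anticancer therapy.

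Two neighbouring paragraphs matter. The one on eosinophil counts already analyses change in eosinophils, including longitudinal models against skin-event grade. The one on RDI calculates the relative dose intensity of the culprit drug for each patient over the study, from clinicians' notes and the medical record, and adds regression models for compliance.

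**The concern.** The heading promises an answer about cancer treatment, but the variable is a pharmacodynamic marker of the study drug. Section 3.0 puts having to pause or stop cancer treatment first among several harms of these skin events, and part of its rationale for benralizumab is that such pauses could be avoided. A reader of the results would look to this endpoint for evidence of that.

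Followed as written, the paragraph would yield a mean, standard deviation and range of eosinophil change. A large fall could be presented as a favourable effect on later cycles although the figure says nothing about whether those cycles took place.

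**Working it through.** The plan gives no sample size, power or target for this endpoint, so there is no figure to reproduce. The check sets the objective against each reported quantity.

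**Inputs**
- Entry count: Section 6.1 requires a "cutaneous adverse event defined as any cutaneous reaction listed below and blood eosinophil counts of at least .3 K/mcl", which is 300 cells/µL or more.
- Drug effect: Section 3.0 (Benralizumab) reports that in Trials 1 and 2 "blood eosinophils were reduced to a median absolute blood eosinophil count of 0" cells/µL at the first observed time point, 4 weeks, and that this lasted through treatment. These were asthma patients.
- A less complete depletion for comparison: the same section gives a median of 50 cells/µL at Week 40 in the 20 mg group of the dose-ranging asthma trial.
- Number of planned culprit cycles: not stated. I assume 6 for illustration; the result does not depend on it.

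**1. Eosinophil change.** Percent change = 100 × (post − entry) / entry. The entry counts of 700 and 1500 are the cut-points that Section 3.0 cites for DRESS scoring.
- Post = 0: entry 300 gives 100 × (0 − 300)/300 = −100%. Entry 700 (change −700) and entry 1500 (change −1500) also give −100%.
- Post = 50: entry 300 gives 100 × (50 − 300)/300 = −83%. Entry 700 gives 100 × (50 − 700)/700 = −93%. Entry 1500 gives 100 × (50 − 1500)/1500 = −97%.

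The number of cycles delivered does not enter the formula. With the post-dose count fixed by the study drug, the result is the same for 6/6, 3/6 or 0/6 cycles given.

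**2. Direction.** Section 3.0 says that drug-related eosinophilia without systemic involvement generally "resolves upon drug discontinuation". If depletion by benralizumab is incomplete, stopping the culprit drug could therefore deepen the fall. The outcome that the trial hopes to avoid could then register as a better result.

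**3. Number scheduled.** Section 6.1 requires cancer patients to intend to stay on the culprit drug. Being scheduled is thus close to an entry condition, and it does not show that a dose was received.

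**4. Timing.** Section 10.0 specifies "Phlebotomy for CBC w differential at every visit", and the visits listed there are study visits. Nothing ties a count to a culprit-cycle date, so the later end of the comparison has no defined time point.

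**5. What RDI adds.** RDI is one ratio of delivered to standard dose per patient. It would fall if culprit drugs were stopped. As specified it does not give the number of cycles delayed or omitted or the proportion of patients who continued. The paragraph also has no rule for recording why a dose was held.

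**The case against.** The strongest reply is that the trial does measure drug delivery elsewhere. RDI and compliance form a separate secondary objective with their own analysis. If every culprit drug were stopped, RDI would be low and would show it. Other planned data help at the margin: concomitant medication review at every visit, oncology visit data gathered at the last study visit (for immune-related events), and a summary of reasons for leaving the study. This stands. A reader might infer that a claim of continued anticancer treatment would have no data behind it; the documents do not support that.

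Three further limits also stand.
- The −100% figure borrows a median from asthma trials. Depletion in patients on checkpoint inhibitors or targeted drugs may differ.
- The plan does not say whether cycles means planned dates or cycles actually given. On the second meaning, a patient with no cycles contributes no value, so a favourable change would not be reported for that patient.
- The plan does not say that RDI will pool holds for rash with holds for other reasons. It is silent on reasons.

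Finally, this is a descriptive secondary endpoint with no test or decision attached. That limits the consequence. It does not make the stated analysis fit its objective: none of these other sources supplies a cycle-level or continuation analysis, and the protocol itself lists subsequent cycles and RDI as separate objectives.

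**Conclusion.** The concern holds for this one endpoint. The stated analysis cannot show whether culprit cycles were given, delayed, reduced or stopped, because it records eosinophil change and scheduling and neither is delivery. If depletion here matches the cited asthma trials, the eosinophil result is about −100% regardless of delivery; with a residual count of 50 it is about −83% to −97% over the entry counts shown. These figures are illustrations. The mismatch between objective and variable needs no assumption about the size of depletion.

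The conclusion goes no further. RDI and compliance will show much of the delivered dose. What is missing is a cycle-level account, the proportion of patients who continue, and the reasons for holds and stops. Nor does Section 3.0 call treatment interruption the main harm; it lists it first among several. The paragraph should be changed because it is wrong for its purpose, but the primary endpoint is not affected.

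**What to change.** In the Section 14.1 paragraph on subsequent planned cycles, replace eosinophil change and number scheduled with:
- (a) the number and proportion of planned culprit cycles from Week 0 that were given on time at full dose, delayed, reduced or omitted;
- (b) the proportion of patients with any hold, reduction or permanent stop because of the skin event, shown separately from other reasons such as cancer progression or other toxicity, with exact binomial confidence intervals.

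Cycles cluster within patients, so (a) is best left descriptive; the binomial interval belongs to the patient-level proportion in (b). State in advance what counts as a planned cycle for each culprit drug and what counts as on time. Let (b) also serve the ability-to-continue endpoint, report both beside RDI, and keep eosinophil change in its own paragraph.

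The source is the set of notes and records already abstracted for RDI. The cost is a wording change plus one reason code for each culprit-drug change. That is some extra abstraction, because the RDI paragraph mentions only dosage. No visit, dose or clinical rule changes.

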## 6.2 Participant Exclusion Criteria

- Concurrent use of another investigational drug or device for the ercAE (i.e., outside of study treatment) during, or within 4 weeks of treatment.
- Patients receiving prednisone  $\geq$  20mg a day.
- Known use of anti-IL-5 agents or biologics for the treatment of asthma which are known to decrease blood eosinophil levels.
- Patients cannot use new topicals or medications for indication of pruritus or skin rash
- Known history of anaphylaxis to biologic therapy
- A helminthic parasitic infection diagnosed within 24 weeks prior to the first treatment, that had not been treated with, or has failed to respond to, standard of care therapy.
- Known history of human immunodeficiency virus (HIV) infection or current chronic or active hepatitis B or C infection requiring treatment with antiviral therapy.
- Active infection that would impair the ability of the patient to receive study treatment.
- Women who are pregnant or breast-feeding.

- Any condition which, in the investigator's opinion, makes the subject unsuitable for trial participation.
- Receipt of live attenuated vaccines 30 days prior to the date of randomization
  - Receipt of inactive/killed vaccinations (e.g., inactive influenza) is allowed provided they were not administered within 1 week before/after any investigational product administration.
- Known history of allergy or reaction to the investigational product formulation

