### 13.2 Criteria for Study Endpoint Evaluability

Patients who are removed from the study prior to starting Benralizumab will be considered inevaluable and replaced. Patients who receive at least one dose of Benralizumab will be included in the evaluation of the primary objective if they have a post-therapy documented clinical response. Patients who progress and are placed on agents instead of or in addition to the culprit agents will be removed from the study. Patients who receive steroids at doses greater than prednisone 20mg a day or equivalent or other immunosuppressive agents to manage additional irAEs will be considered a failure for the primary endpoint.

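### Corticosteroid-naïve status is set, as written, by steroid use in the 14 days after the first dose, while the comparison group is fixed at study start by prednisone dose

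*Combined protocol and SAP*

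**What the plan says.** Section 2.0 lists this secondary objective: "To compare the effect of benralizumab on corticosteroid naïve and corticosteroid dependent/refractory ercAEs". Section 14.1 (Secondary endpoints) defines the two groups:

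- Naïve: "Corticosteroid naïve patients are those not receiving corticosteroids for 14 days since Week 0/Day 1 of benralizumab treatment".
- Dependent/refractory: "Corticosteroid dependent/refractory ercAEs are patients that are on prednisone 10mg a day or greater at the initiation of study".

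The planned analysis is to count each group and to "measure change in blood eosinophil levels between Week 0/Day 1 and Week 8/Day 56, report descriptive statistics such as mean, standard deviation and range". No test is planned, and ercAE response is not tabulated by group.

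Three other provisions bear on the point.

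- Section 6.2 excludes "Patients receiving prednisone $\geq$ 20mg a day".
- Section 13.2 says that patients given more than prednisone 20 mg/day (or equivalent), or other immunosuppressants, "to manage additional irAEs will be considered a failure for the primary endpoint".
- Section 14.1 also makes steroid need an outcome: "The proportion of patients requiring supportive medications such as corticosteroids, antihistamines and immunosuppressants will be reported at each time point".

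**The concern.** A subgroup used to compare treatment effect should be fixed before treatment can influence who belongs to it. On the literal wording, the naïve group is known only at Day 14, after the first injection has had two weeks to act. The other group is known at entry, so the two are selected by different rules.

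The same event is also treated in three ways. A corticosteroid start between Day 1 and Day 14 is an outcome in the supportive-medication analysis. It is a failure in the primary analysis if the dose exceeds 20 mg/day for an additional irAE. In this comparison it is a reason to leave the naïve group.

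The dependent/refractory label has a separate weakness. It rests on dose alone, with nothing on failed response, failed taper or duration. Section 3.0 names steroid-dependent/refractory patients as those with no further options, so readers will give this group weight.

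**Working it through.** **1. The two definitions side by side.**

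| | Naïve | Dependent/refractory |
|---|---|---|
| Information used | Corticosteroid use over 14 days counted from Day 1 | Prednisone dose at study start |
| Known at | Day 14 | Entry |
| Can change after the first dose | Yes | No |
| Route | Not stated | Prednisone |
| Failed response or taper required | Not applicable | No |

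No other section gives a baseline definition of naïve or says where a patient who starts steroids between Day 1 and Day 14 belongs.

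**2. Who falls where.** The Section 14.1 floor of 10 mg/day and the Section 6.2 exclusion at 20 mg/day together make the dependent/refractory group 10 to <20 mg/day. A patient steroid-free on Day 1 who starts by Day 14 is in neither group. Nor is a patient who enters on more than 0 but less than 10 mg/day and continues. Because route is not stated for the naïve group, a patient continuing a topical steroid, as Section 6.1 requires of established users, might also be disqualified.

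**3. Effect on the planned outcome (eosinophil change).** The plan states no figure for this comparison, so there is none to reproduce. Let q be the share of Day 1 steroid-free patients removed, R the mean percent change in those retained and M the mean in those removed. The full-group mean is (1−q)R + qM, and the observed mean is R. The shift is therefore R − [(1−q)R + qM] = q(R − M).

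The documents give neither q nor R − M. Assumed values:

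- q = 4%, gap 5 to 20 percentage points: shift 0.04 × 5 = 0.2 to 0.04 × 20 = 0.8 points.
- q = 10%, same gap: shift 0.10 × 5 = 0.5 to 0.10 × 20 = 2.0 points.

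The sign can go either way. Early steroid starters may have responded less to benralizumab, but the steroid may itself lower their count (also an assumption). Section 3.0 reports a median count of 0 cells/µL at 4 weeks in the asthma trials. If depletion is similar here, R − M would be small.

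**4. Effect if ercAE response were also tabulated by group.** Let p be the true response rate, equal in both groups, and f the share of naïve non-responders who start steroids by Day 14. The share leaving is (1−p)f, and the observed naïve rate is p / [1 − (1−p)f]. The values of p run from the plan's 40% reference rate to its 70% expected rate; f is assumed.

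| p | f = 10% | f = 25% | f = 50% |
|---|---|---|---|
| 0.40 | 0.40/0.94 = 42.6% (+2.6) | 0.40/0.85 = 47.1% (+7.1) | 0.40/0.70 = 57.1% (+17.1) |
| 0.60 | 0.60/0.96 = 62.5% (+2.5) | 0.60/0.90 = 66.7% (+6.7) | 0.60/0.80 = 75.0% (+15.0) |
| 0.70 | 0.70/0.97 = 72.2% (+2.2) | 0.70/0.925 = 75.7% (+5.7) | 0.70/0.85 = 82.4% (+12.4) |

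For this outcome the direction is fixed: only non-responders leave, so the naïve rate rises. With both groups fixed on or before Day 1, the artefact is zero.

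**The case against.** Four things can fairly be said in the plan's defence.

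- *Since* may be a slip for *before*. Naïve normally describes prior exposure, and the paired definition refers to study start. This is plausible, but the text does not say so, and an analyst following it would apply a post-dose rule. Correcting the word would cure the selection problem. It would not cure the dose-only label or the unplaced patients.
- Section 6.2 bars new topicals or medications for rash or pruritus, so the obvious route, prednisone for a worsening rash, is restricted. This stands as a limit on size. It does not close the route, because Section 13.2 foresees steroids for additional irAEs and Section 14.1 tracks steroid need at every time point.
- The comparison is descriptive, on eosinophils, and does not touch the primary endpoint. This stands.
- The plan does not say that the two groups should cover everyone, and the upper limit of 20 mg/day is a disclosed eligibility rule. Both points stand. The unplaced patients are a reporting gap, and the narrow dose band is a matter of labelling.

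A reader might infer from the response table that the trial will report a spurious naïve advantage of 5 to 15 points or more. The documents do not support that. Response by steroid group is not planned, and shares as high as 50% starting steroids within two weeks have no basis in the text.

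**Conclusion.** The point holds in a limited form. As written, one side of a stated secondary comparison is selected on an event after the first dose and the other is not. That rests on the wording alone and needs no assumption beyond a literal reading.

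The size is unknown. For the planned eosinophil summary, the shift is 0.2 to 2.0 percentage points under the assumed inputs, in either direction, and smaller still if depletion is near complete. If response were added by group, the naïve rate would be inflated by roughly 2 to 7 points for f between 10% and 25%.

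It would go too far to say that the naïve result is known to be biased upwards, since the direction is fixed only for an outcome that the plan does not tabulate by group. The primary endpoint is unaffected. This should be corrected, but it is a wording matter in a descriptive secondary analysis.

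**What to change.** - Define naïve status from corticosteroid exposure in a stated window ending on or before Day 1, before the first dose; for example, none in the 14 days before Day 1. State whether only systemic steroids count. With a short window, a patient who failed steroids and stopped earlier still counts as naïve, so choose the length with that in mind.
- Keep every dosed patient in the Day 1 group. Report steroid starts after Day 1 in this context only as the supportive-medication outcome.
- Call the present 10 mg/day group what it is, on prednisone 10 to <20 mg/day at entry, and reserve dependent/refractory for patients whose medical history documents steroid failure or a failed taper. A rule based on having a grade 2/3 event while on steroids would not work: Section 6.1 requires grade 2/3 at entry, so anyone on a systemic steroid on Day 1 would qualify.
- Report patients in neither group as a third category.

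The cost is SAP wording, with no new visit, sample or patient. Section 11.0 already schedules medical history at screening and medication review at screening and Day 1, but the documents do not say that earlier steroid response or taper failure is recorded, so some chart abstraction may be needed. The naïve group's composition will change, and its result may look less favourable.
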